- On active treatment with high-dose corticosteroids (i.e., ≥ 20 mg prednisone or equivalent per day when administered for ≥ 2 weeks), as well as any FDA approved alkylating agents, antimetabolites, transplant-related immunosuppressive drugs, cancer chemotherapeutic agents classified as severely immunosuppressive, tumor-necrosis (TNF) blockers, and other biologic agents that are immunosuppressive or immunomodulatory (e.g., B-cell depleting agents) or any combination of these agents.
- Previously treated but not on active treatment as defined in Section 8.1.

The patient's clinical stability will be defined by the Investigator at the time of enrollment and applies to all solid tumor or hematologic malignancy patients. The categories for clinical stability are: (1) in remission, (2) stable or (3) progressing. These assessments of clinical stability will be repeated at month 3 and month 6 of patient follow-up. Hematologic malignancy patients may be enrolled even if their therapy is completed and their cancer status is considered stable or in remission. Solid tumor patients are excluded if their therapy has been completed more than 6 months prior to baseline and their cancer is either stable or in remission. All solid tumor or hematologic malignancy patients may be enrolled if their cancer status is considered as progressing, whether or not they are on active treatment. Enrolled patients will also fulfill one of the following criteria: (1) they have received any SARS-CoV-2 vaccination with an FDA EUA vaccine (Janssen, Moderna or Pfizer) and do not wish to receive an additional vaccine dose, or (2) they have received any SARS-CoV-2 vaccination with an FDA EUA vaccine (Janssen, Moderna or Pfizer) and wish to receive an additional Janssen, Moderna, Pfizer vaccine dose.

The baseline evaluation will require SARS-CoV-2 specific RBD-IgG antibody testing in all vaccinated participants who are at least 4 weeks post their most recent vaccine dose. To qualify for enrollment into the program, each solid tumor cancer patient must be either on active treatment, up to 6 months post-treatment and/or has progression of his/her cancer. Hematologic malignancy patients may be enrolled on active treatment or up to 12 months post- treatment and if their cancer is in remission, stable or progressing.

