
8.0 Patient Eligibility Criteria
	
8.1 Inclusion Criteria Patients will be considered qualified for study enrollment if they meet the following inclusion criteria:
 
 ➤ Male or Female gender at birth ➤ Women who are not pregnant, not breast feeding and of child-bearing potential using contraception prior to enrollment in the study. Women of child-bearing potential must agree to continued use of contraception throughout the 12 months of study participation. ➤ Age at least 18 years ➤ It is preferable that a patient has access to a “smartphone” or tablet or laptop or desktop computer and/or an email address ➤ In the event that a patient does not have access to any of the above, the patient may complete all follow-up surveys via the study’s Call Center or in written form in the offices of the Principal Investigator as specified in the protocol

- Documented diagnosis of either hematologic malignancy or solid tumor as identified by standard ICD-10 diagnostic category
- Patients may be included with at least ONE of the following criteria:
 - **On active treatment** for solid tumor or hematologic malignancies. This can include: high-dose corticosteroids (i.e., ≥ 20 mg prednisone or equivalent per day when administered for ≥ 2 weeks), as well as any FDA-approved alkylating agents, antimetabolites, transplant-related immunosuppressive drugs, cancer chemotherapeutic agents classified as severely immunosuppressive, tumor-necrosis (TNF) blockers, and other biologic agents that are immunosuppressive or immunomodulatory (e.g., B-cell depleting agents) or any combination of these agents. For patients on active oral, IM or IV therapy at the time of enrollment, treatments may have been initiated at any time prior to baseline
 - Hematologic malignancy patients may be included up to 12 months post-last day of last cycle of treatment with oral, IV, or IM therapy and either in remission, stable or progressing as determined by the Investigator
 - Solid tumor patients may be included up to 6 months post-last day of last cycle of treatment with oral, IV, or IM therapy and either in remission, stable or progressing as determined by the Investigator
 - Received chimeric antigen receptor (CAR-T) or hematopoietic stem cell transplant (within 2 years of transplantation or taking immunosuppression therapy)

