8.2 Exclusion Criteria

Patients meeting any of the following criteria will be excluded from study participation:

- Women who are pregnant, breast feeding or of child bearing potential and not using contraception
- Absence of a qualifying type of cancer as defined by standard ICD-10 diagnostic criteria
- Patient receiving only radiation therapy
- Patient with an ECOG performance status of 2 or higher

- Patient with an expected cancer survival of less than 12 months by disease category
- Patient receiving adjuvant endocrine therapy as their only form of therapy for early-stage breast cancer
- Solid tumor patients more than 6 months post treatment and their cancer is considered to be stable or in remission as determined by the Investigator
- AZD7442 administration at any time prior to day of enrollment
- Have a positive test for SARS-CoV-2 antigen performed by either Rapid Test or SARS-CoV-2 RNA by RT-PCR (Polymerase Chain Reaction) less than 90 days prior to enrollment
- Patient with a prior (within 90 days), current, or planned use of any of COVID-19 convalescent plasma, other monoclonal antibodies against SARS-CoV-2 or any other EUA approved SARS-CoV-2 treatment
- Patient with fever >100.0 F, and/or cough, chills, loss of smell or taste or shortness of breath or any other signs or symptoms consistent with COVID-19 within 5 days prior to enrollment
- Patient who has any known active acute respiratory infection
- Patient who has persistent (refractory to treatment for ≥ 14 days) bacterial or fungal infection
- Patient who has a past SARS-CoV-2 infection within 90 days prior to randomization
- Patient who has received vaccination with any dose of Janssen, Pfizer or Moderna COVID-19 vaccine less than 14 days prior to baseline for this study
- Planned use of any investigational, authorized, or approved vaccine for COVID-19 less than 14 days prior to administration of AZD7442 600 mg IM or IV
- Patient who is unwilling to have SARS-CoV-2 RBD-IgG antibody levels drawn at least 5 times
- Patient who is unwilling to receive treatment with IM or IV AZD7442
- Patient who is unwilling to complete baseline and up to 14 follow-up Experience/Clinical Outcome Assessment (COA) surveys.

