
17.0 Statistical Considerations
	
17.1 Sample Size Estimation
 
This program will recruit approximately 1,500 treated cancer patients divided into approximately 1,200 qualified solid tumor and 300 qualified hematologic malignancy patients from approximately 75 hematology/oncology medical practice locations throughout the United States. It is expected that on average, each site will enroll 16 solid tumor and 4 hematologic malignancy patients.
 
17.2 Sample Size Power
 
With a sample size of 1500 patients, the power to detect a non-inferiority margin of 5 mcg/ml with a standard deviation of 25 mcg/ml and Type I error rate of 1% is estimated to be approximately 80% when comparing the serum concentration levels between solid tumor and hematologic malignancy groups. The assumed comparison is between 1200 solid tumor and 300 hematologic malignancy patients. A target sample of 1500 patients will provide adequate size to analyze all of the secondary endpoints identified in the baseline and follow-up patient experience/COA surveys and the QoL surveys.
 
At the time of interim analysis, the power to detect a 5 mcg/ml non-inferiority margin with a standard deviation of 25 mcg/ml and Type I error rate of 1% is estimated to be approximately 45%. This assumes a sample of 600 solid tumor and 150 hematologic malignancy patients.
 
17.3 Stratification
 
This is an open-label, pragmatic, multi-center study of participants receiving AZD7442 600 mg IM or IV for prevention of symptomatic SARS-CoV-2 infection including SARS-CoV-2 related hospitalization and/or SARS-CoV-2 related death.

Patients will be stratified based on type of cancer (solid tumor vs hematologic malignancy) with additional stratification for concomitant treatment regimen of chemotherapy only, immunotherapy only, targeted therapy only and other therapy/combination therapy. It is assumed that 80% of enrolled cancer patients will have solid tumors. Patients will be sub-stratified by: currently on active treatment, ≤ 3 months post-treatment or > 3 months and ≤ 12 months post-treatment.

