17.6 Evaluations of Primary and Secondary Endpoints

The primary and secondary endpoints will be evaluated for the intent-to-treat and per protocol patient populations. The primary comparisons will be the serum concentration of AZD7442 at Days 30, 90, 180, 270 and 360 post-baseline. Serum concentration comparisons of the log-adjusted serum AZD7442 concentration will be analyzed using linear mixed models for repeated measures. Models will include disease category, overall dose, and dose/kg accounting for concomitant treatment regimen category along with appropriate treatment and time interactions. An unstructured covariance matrix will be assumed, however, in the event of non-convergence, compound symmetry, and AR (1), covariance structures will be attempted, in that order. The Least Square Means Differences, and their 95% CIs, will be reported for each timepoint (e.g., Days 30, 90, 180, 270, and 360 post-treatment).

Additional comparisons for Quality of Life (QoL) will be made between the disease category cohorts and concomitant treatment regimen categories. The disease category cohorts are solid tumor cancers and hematologic cancers. Concomitant treatment regimen categories will be defined as chemotherapy only, immunotherapy

only, targeted therapy only, other therapy/ combination therapy only. Differences in the primary endpoints will be assessed using a two-sided statistical significance level of 0.01, adjusting for planned multiple comparisons. All other differences will be assessed using a two-sided statistical significance level of 0.05.

The secondary endpoint comparisons will be made:

- between concomitant treatment regimen categories and
- between disease category cohorts

The between concomitant treatment regimen categories will account for the between disease category analyses. These secondary endpoint comparisons will be made using a logistic regression or linear mixed model accounting for potential patient and disease factors where appropriate. Additional secondary endpoints are as noted previously. The secondary endpoints will be analyzed for the Intent-To-Treat (ITT) population with a Per-Protocol (PP) sensitivity analysis.

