	
17.10 Breakthrough Infection Descriptive Analysis
 
All patients who experience a symptomatic breakthrough SARS-CoV-2 infection, defined as a positive SARS-COV-2 RNA by RT-PCR test with or without viral genomics and/or symptomatic clinical evidence of SARS-CoV-2 disease, will have a descriptive analysis that includes a clinical outcome (e.g., symptomatic infection, SARS-CoV-2 related hospitalization and/or SARS-CoV-2 related death), a profile of neutralizing antibody as measured by serum concentration of AZD7442, a functional analysis of T- characterized by cytokine stimulation and secretion and a genomic sequencing of the virus. In addition, relationship between these data and World Health Organization Ordinal Scale for Severity of SARS-CoV-2 Disease will be performed.
 
17.11 Patient Demographics, Disease and Treatment Attributes
 
Baseline patient characteristics for all enrolled participants include age, gender, race, weight and Body Mass Index (BMI) and will be analyzed using descriptive statistics for all strata and sub-strata. Patient demographics, disease and treatment attributes will be summarized and compared between the disease category cohorts and concomitant treatment regimens. Any attributes with significant differences will be considered for inclusion as factors in logistic regression and linear model analyses. Disease attributes will include stage of disease, time from initial diagnosis and performance status will be assessed. Treatment regimen attributes including type of therapy, cycle at time of study enrollment and cycle duration will be summarized.
 
17.12 Statistical Models
 
Statistical considerations for other endpoints will be treated on a case-by-case basis depending on the nature of the outcome variables and their distributions. Such approaches may include χ^2 cross-tabulations, t-tests, ANOVAs, negative-binomial regressions, logistic regressions, mixed model for repeated measures and linear regression.

18.0
	
18.1 Identification of Non-Serious and Serious Adverse Events

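### The concentration model in 17.6 leaves out treatment timing, so the solid-versus-hematologic contrast is open to confounding by time since therapy

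*Protocol*

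**What the plan says.** **Model terms.** Protocol section 17.6 specifies a linear mixed model for repeated measures on log-adjusted AZD7442 concentration: "Models will include disease category, overall dose, and dose/kg accounting for concomitant treatment regimen category along with appropriate treatment and time interactions". The only therapy-related term is regimen category, which the same section defines by type of therapy alone: "Concomitant treatment regimen categories will be defined as chemotherapy only, immunotherapy" only, targeted therapy only, or other/combination therapy.

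**Timing as a design element.** Section 17.3 states: "Patients will be sub-stratified by: currently on active treatment", up to 3 months post-treatment, or more than 3 and up to 12 months post-treatment. Section 1.1 names this among the three elements on which the design rests, and sections 5.3 and 6.3 repeat it. Section 14.1 uses it for a secondary comparison of infection incidence, but not for concentration.

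**Eligibility windows.**
- Section 8.1, hematologic: "Hematologic malignancy patients may be included up to 12 months post-last day of last cycle of treatment".
- Section 8.1, solid tumor: "Solid tumor patients may be included up to 6 months post-last day of last cycle of treatment", whether in remission, stable or progressing.
- Section 8.2 excludes: "Solid tumor patients more than 6 months post treatment and their cancer is considered to be stable or in remission".
- Section 5.2, on progressing disease with or without ongoing treatment: "All solid tumor or hematologic malignancy patients may be enrolled if their cancer status is considered as progressing, whether or not they are on active" […].

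**Route for further covariates.** Section 17.11: "Any attributes with significant differences will be considered for inclusion as factors in logistic regression and linear model analyses". The treatment attributes it lists are type of therapy, cycle at enrollment and cycle duration.

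**Status of the contrast.** Sections 3.2 and 14.1 list solid-versus-hematologic concentration as secondary. Section 17.2 bases the study's power on it.

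**The concern.** Disease category is not assigned at random, so the two groups can differ in anything related to drug level. Here the eligibility rules themselves create one such difference. A hematologic patient in remission 9 months after the last cycle can enter; a solid tumor patient in the same position cannot. The hematologic group can therefore contain stable or remitted patients at 6 to 12 months off therapy who have no counterpart in the solid tumor group.

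If active therapy, or recovery from it, affects AZD7442 concentration, a disease-category term in a model without timing absorbs part of that effect. A difference could then be credited to disease type when it reflects time since treatment, or a real difference could be hidden. The regimen term does not help, because it records what was given and not when it ended.

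**Working it through.** **1. The plan's own figure.** Inputs from section 17.2: SD 25 mcg/ml, margin 5 mcg/ml, 1,200 solid and 300 hematologic patients, type I error 1%.

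- Standard error = 25 × √(1/1200 + 1/300) = 1.614 mcg/ml.
- Power, one-sided 1% = Φ(5/1.614 − 2.326) = 78.0%, against a stated figure of about 80%.
- Interim, 600 versus 150: standard error 2.282; Φ(5/2.282 − 2.326) = 44.6%, against a stated 45%.

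The stated figures thus fit a one-sided 1% test. The two-sided 0.01 level in section 17.6 would give 69.9% and 35.0%. The present point does not depend on that difference; the one-sided reading is used below because it is the closer match.

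**2. Size of a possible bias.** The protocol gives neither the timing mix in each group nor any effect of timing on concentration, so both are assumed. With no timing term:

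bias = (difference between groups in the share long off treatment) × (shift in concentration for that status)

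With an assumed shift of 5 mcg/ml:

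| Difference in share | Bias (mcg/ml) | Power if bias is adverse, Φ((5 − b)/1.614 − 2.326) | Error at the margin if favourable, 1 − Φ(2.326 − b/1.614) |
|---|---|---|---|
| none | 0 | 78.0% | 1.0% |
| 10 points | 0.5 | 67.8% | 2.2% |
| 20 points | 1.0 | 56.1% | 4.4% |
| 30 points | 1.5 | 43.7% | 8.1% |

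A wider range of assumptions (10 to 40 points, 2.5 to 10 mcg/ml) gives a bias of 0.25 to 4.0 mcg/ml. All of this is on the raw scale of section 17.2, whereas the section 17.6 model works on log concentration. The table is an illustration, not an estimate.

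**3. Would the existing three-level sub-stratum be enough?** Its last level pools 3–6 months with 6–12 months, and the eligibility rules differ at 6 months. Assume this mix:

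| | Active | ≤3 months | 3–6 months | 6–12 months |
|---|---|---|---|---|
| Hematologic | 50% | 15% | 15% | 20% |
| Solid tumor | 60% | 20% | 20% | 0% |
| Shift (mcg/ml) | 0 | 1 | 3 | 5 |

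- No timing term: hematologic mean shift = 0.15×1 + 0.15×3 + 0.20×5 = 1.60; solid = 0.20×1 + 0.20×3 = 0.80; bias 0.80.
- Three-level sub-stratum: within the last level the hematologic mean is (0.15×3 + 0.20×5)/0.35 = 4.14 and the solid mean is 3, a gap of 1.14. The other two levels have no gap. Weighting each level by n_h·n_s/(n_h + n_s) gives weights 124.1, 37.9 and 73.0, so bias = 73.0 × 1.14/235.1 = 0.36.
- Four levels, split at 6 months: bias 0.

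With shifts 0/2/5/10 the three results are 1.65, 0.89 and 0. If 5% of solid tumor patients are progressing and beyond 6 months (leaving 15% at 3–6 months), the first set of shifts gives 0.70, 0.20 and 0. The sub-stratum as defined removes part of the bias; a split at 6 months removes it in these examples.

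**4. Would the section 17.11 screen catch the imbalance?** With 1,200 versus 300 patients and a test at p < 0.05 (an assumed threshold), a 10-point difference is flagged 87% to 99.9% of the time for solid-group shares of 5% to 50%. Differences of 20 to 30 points are flagged essentially always. An imbalance of 0.15 SD, smaller than any in the table under step 2, would be flagged Φ(0.15/0.0645 − 1.96) = 64% of the time.

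**The case against.** **The list may not be exhaustive.** The protocol does not say that the 17.6 terms are the only ones, and a full covariate list often sits in a statistical analysis plan, which is not at hand. Section 17.6 also lets secondary comparisons account for patient and disease factors where appropriate, and 17.11 opens the linear models to further attributes. This stands in part: nothing bars timing. But 17.6 does state a list, the list leaves out a factor the protocol stratifies by, and neither clause names time since therapy or commits to using it.

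**The imbalance would be noticed.** A reader might infer that significance screening would miss it. For imbalances large enough to matter in the illustration, step 4 shows the opposite, provided timing is among the attributes tested. The weakness is that section 17.11 does not list timing, and that a flagged attribute is only considered.

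**Solid tumor patients are not all confined to 6 months.** A reader might infer from section 8.1 that none enters later. The documents do not support this: 8.2 excludes only stable or remitted patients beyond 6 months, and 5.2 admits progressing patients on or off treatment. The structural imbalance is confined to stable or remitted patients.

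**Confounding is not shown.** It is tempting to say that the contrast *is* confounded. That requires time since therapy to affect AZD7442 concentration, which the protocol neither states nor quantifies, and the assumed 5 mcg/ml shift equals the whole margin. Only openness to confounding is supported.

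**The contrast is secondary, and comparing the cohorts as enrolled is a legitimate descriptive aim.** Both are true. Yet 17.2 powers the study on this contrast, so how it is adjusted should be settled in advance.

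**Conclusion.** The point holds as a gap in the stated model. Section 17.6 omits treatment timing, which the protocol treats as a design element. The eligibility windows make timing differ systematically between stable or remitted hematologic and solid tumor patients, in a non-randomised contrast that carries the power calculation.

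The consequence is potential confounding of unknown size. Under the assumed 10 to 30 point difference in mix and 5 mcg/ml raw-scale effect, the bias would be 0.5 to 1.5 mcg/ml, or 10% to 30% of the margin. It would be zero if timing has no effect on concentration. The primary objective, describing concentration in all patients, does not depend on this contrast. The omission should be corrected because the remedy is cheap and is credible only if specified in advance.

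**What to change.** 1. **Section 17.6.** Pre-specify time since last treatment as a fixed factor, with its interaction with visit, in the concentration model. Use four levels: active, ≤3, >3 to ≤6, and >6 to ≤12 months. Active status plus continuous time since last treatment would also serve. The existing three levels are not sufficient, for the reason in step 3.
2. **Section 17.6.** Add a sensitivity analysis of the solid-versus-hematologic contrast restricted to patients on treatment or at most 6 months post-treatment, where both groups are eligible whatever their disease status.
3. **Section 17.11.** State that this factor is included whether or not the groups differ significantly at baseline. Other attributes may still be considered as now.
4. **Sections 5.2, 8.1 and 8.2.** Reconcile the passages on solid tumor patients beyond 6 months, so that it is clear who can populate the last level. Which rule applies is for the sponsor to settle.

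Cost: a few more model parameters in about 1,500 patients, one extra analysis and some wording. Assigning the sub-stratum already requires the treatment end date or its equivalent. The remaining limitation is that few solid tumor patients are likely to fall in the >6 month level, so adjustment there will rest on little information; the restricted analysis covers that gap.

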9.3 Follow-Up Activities

Follow-Up activities are as follows:

- At Day 180 post-baseline, all patients will be administered a repeat dose of AZD7442 600 mg IM or IV. The window for this treatment will be +/- 5 days from the actual due date. The dose will be administered in the same manner as the baseline dose unless patient circumstances require a different route of administration. All requirements listed above for baseline AZD7442 administration both IV and IM will be followed for the repeat dose including the one-hour post-dose observation period.
- Patients will complete follow-up Patient Experience/COA surveys on days 2, 30, 60, 90, 120, 150, 180, 181, 210, 240, 270, 300, 330 and 360 post-baseline at home. The window for these surveys will be +/- 5 days from the actual survey due date except for day 2 survey which is +5 days only.
*NB - Study participants will complete all surveys via mobile phone, desktop, laptop, tablet computer or via Call Center. The study site is not responsible for patient completion of the surveys.
- Patients will complete QoL assessments on days 2, 30, 90, 180, 270, and 360 post-baseline at home. The window for these assessments will be +/- 5 days from the actual due date except for day 2 assessment which is + 5 days only.
- Site personnel will obtain blood for serum concentration of AZD7442 at days 30, 90, 180, 270 and 360 post-baseline in the office for all patients. The window for these blood draws will be +/- 5 days from the actual due date. All

serum concentration measurements will be sent to PPD Bioanalytical Laboratory in Richmond, VA for analysis.

- Site personnel will obtain blood for RBD-IgG antibody level at days 90, 180, 270 and 360 post-baseline in the office for all patients. The window for these blood draws will be +/- 5 days from the actual due date. All RBD-IgG antibody levels will be sent to LabCorp for analysis.
- Site personnel will obtain blood for T-cell assay at Day 30 post-baseline in the office for all patients and send to Isoplexis in Branford, CT for analysis. A subset of patients will be selected including 120 patients with hematologic malignancy and 60 patients with solid tumors in order to have site personnel obtain blood for repeat T-cell assay at Day 210 post-baseline in the office and send to Isoplexis in Branford, CT for analysis. The window for these blood draws will be +/- 5 days from the actual due date.

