13.1 Primary Endpoint

The study's primary endpoint will assess AZD7442 serum concentration collected on days 30, 90, 180, 270, and 360 post-baseline in all patients.

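### Minor: if the unstructured matrix fails, Section 17.6 falls back to two structures with one variance for all visits, which would misstate the per-visit standard errors if log-scale spread changes over the dosing interval

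*Protocol*

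**What the plan says.** Protocol Section 13.1 defines the primary endpoint as serum concentration "collected on days 30, 90, 180, 270, and 360 post-baseline in all patients". Section 17.6 gives the model: "Serum concentration comparisons of the log-adjusted serum AZD7442 concentration will be analyzed using linear mixed models for repeated measures". The contrasts are visit by visit: "The Least Square Means Differences, and their 95% CIs, will be reported for each timepoint".

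For the covariance, Section 17.6 states "An unstructured covariance matrix will be assumed, however, in the event of non-convergence", and then the order of replacement: "in the event of non-convergence, compound symmetry, and AR (1), covariance structures will be attempted, in that order". No structure with visit-specific variances stands between the unstructured matrix and compound symmetry.

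On the test level, the same section says "Differences in the primary endpoints will be assessed using a two-sided statistical significance level of 0.01, adjusting for planned multiple comparisons"; all other differences are tested at 0.05.

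Section 9.3 adds the second dose: "At Day 180 post-baseline, all patients will be administered a repeat dose of AZD7442 600 mg IM or IV". The five visits therefore span two dosing intervals, with gaps of 60, 90, 90 and 90 days.

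**The concern.** Compound symmetry and AR(1), as normally understood, each have two parameters: one variance and one correlation. The standard error at each visit then rests on a variance pooled over all five visits. That is harmless only if the visits have about the same spread.

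The protocol itself suggests they may not. Section 17.5 predicts a missing Day 180 value from a straight line in log concentration, which implies log-linear decline. Section 1.2 expects comorbidities to affect how well patients keep therapeutic concentrations over 12 months. If log-linear slopes differ between patients, spread widens as time since dose grows, and the Day 180 dose partly resets it. A pooled variance would then make the late-interval contrasts look more precise than they are, and the Day 30 contrast less precise. Tests and 95% confidence intervals at those visits would be wrong in opposite directions.

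**Working it through.** **The plan's own figure.** Section 17.2 gives about 80% power (interim about 45%) for a 5 mcg/ml margin, SD 25 mcg/ml and 1% Type I error. Final SE = 25 × √(1/300 + 1/1200) = 1.614, and 5/1.614 = 3.098. One-sided 1%: Φ(3.098 − 2.326) = 78.0%. Interim SE = 25 × √(1/150 + 1/600) = 2.282, and Φ(2.191 − 2.326) = 44.6%. Both fit the stated figures on a one-sided basis; two-sided 1% gives 69.9% and 35.0%. Sidedness is a separate matter. What counts here is that the only SD in the protocol is one raw-scale value, with nothing by visit or on the log scale.

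**Formula.** Take complete data and a separate mean for each group at each visit. The estimated difference at visit j is then the raw difference in means, with true variance v_j(1/300 + 1/1200). Compound symmetry replaces v_j by v̄, the mean of the five visit variances. The group sizes cancel:

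actual level at visit j = 2[1 − Φ(2.576 × √(v̄/v_j))].

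Equal variances give exactly 1.00%.

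**A worked case (all inputs assumed).** Half-life 90 days, so mean rate k = ln 2/90 = 0.00770 per day; elimination CV 30%, so SD of k = 0.00231; between-patient log SD 0.30; residual log SD 0.10; Day 180 blood drawn before the dose. To first order, v_j = 0.30² + 0.10² + (0.00231 × d_j)². Up to Day 180, d_j is the visit day. After the second dose, d_j = (t − 180) + 180w, with w = e^(−180k)/(1 + e^(−180k)) = 0.25/1.25 = 0.2.

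| Day | d_j | v_j | SD | √(v̄/v_j) | Level of nominal 1% test | Coverage of 95% CI |
|---|---|---|---|---|---|---|
| 30 | 30 | 0.105 | 0.32 | 1.42 | 0.03% | 99.5% |
| 90 | 90 | 0.143 | 0.38 | 1.21 | 0.18% | 98.3% |
| 180 | 180 | 0.273 | 0.52 | 0.88 | 2.4% | 91.5% |
| 270 | 126 | 0.185 | 0.43 | 1.07 | 0.59% | 96.4% |
| 360 | 216 | 0.349 | 0.59 | 0.78 | 4.5% | 87.2% |

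Here v̄ = 0.211. The coverage column uses 1.960 in place of 2.576.

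**Range.** Vary half-life 60-120 days, CV 10-40% and between-patient SD 0.30-0.50, with residual SD 0.10.

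- Mildest corner (120 days, 10%, 0.50): v̄ = 0.2675 against 0.2603, 0.2708 and 0.2772 at Days 30, 180 and 360. Levels: 0.90%, 1.05% and 1.14%.
- Strongest corner (60 days, 40%, 0.30): v̄ = 0.499 against 0.119, 0.792 and 0.954. Levels: below 0.01%, 4.1% and 6.2%. Simulated profiles with log-normal elimination rates, in place of the first-order formula, give 4.5% and 6.2% at Days 180 and 360.

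The range is thus about 1.05-4.5% at Day 180, 1.1-6.2% at Day 360 and 0.00-0.9% at Day 30. AR(1) behaves much the same: on a similar grid (between-patient SD 0.15-0.40, residual SD 0.15) it gave 1.05-4.7% at Day 180 and 1.2-6.5% at Day 360.

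**How likely is the fallback?** Five visits need 5 × 6/2 = 15 covariance parameters, for about 1,500 patients. The interim after six months has three visits, so 3 × 4/2 = 6. In data simulated from this kind of model, the unstructured fit converged in 200 of 200 sets at N = 750 or 1,500 (10% or 30% missing), and in 200 of 200 at each of N = 180 and N = 100. These runs used EM and a simpler mean model than Section 17.6 describes.

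**Does a heterogeneous structure alone cure it?** In four assumed cases with a 90-day half-life, heterogeneous compound symmetry gave about 1.0-1.3% at Days 180 and 360, and heterogeneous AR(1) about 1.0-2.3%. Day 30 stayed at 0.2-0.9%. This is better, but not a full repair: a wrong correlation pattern also shifts the fitted variances. Heterogeneous Toeplitz was not computed.

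**The case against.** The best defence is that unstructured is the planned analysis and the fallback will probably never be used. This largely stands. The PP set is the likeliest weak spot: Section 17.4 requires the Day 210 T-cell assay, which Section 9.3 schedules for only 120 + 60 = 180 patients. But Section 17.4 also requires 75% of serum measurements, at least four of five, so PP data are nearly complete. Failure there has not been shown, and neither has it been excluded for the full model with its dose, regimen and interaction terms. Extra interactions add mean parameters, not covariance parameters.

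A reader might infer that the primary test runs at several times its nominal level. The documents do not support that. They give no half-life, elimination variability or log-scale SD, and near-equal variances would leave the level near 1%. Nor do they support calling the Day 30 test far too strict in general: with a 90-day half-life, CV 10% and between-patient SD 0.30, the level is about 0.6%.

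Three further limits are fair. AR(1) is reached only if two-parameter compound symmetry also fails, so the unequal visit spacing hardly matters. The 1% level is subject to an unspecified multiplicity adjustment, and Section 14.1 lists the solid-versus-hematologic concentration comparison as secondary, where 0.05 may apply. Finally, robust standard errors may be specified in an SAP that is not shown, so their absence here is no fault in itself. What remains is the sequence that the protocol does fix.

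**Conclusion.** The point holds as a minor one. Section 17.6 prescribes a fallback that is valid for per-visit contrasts only if log-scale variance is about constant, and the design gives reason to doubt that. The direction follows from variable elimination: too liberal at Day 360, too liberal at Day 180 if that sample precedes the dose (Section 9.3 does not state the order), and too strict at Day 30. The size rests wholly on assumed pharmacokinetic variability and runs from negligible to several-fold. The unstructured analysis is unaffected, so nothing here impugns the primary result if that fit converges.

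**What to change.** In Section 17.6, place structures with visit-specific variances, for example heterogeneous Toeplitz and then heterogeneous compound symmetry, ahead of or in place of compound symmetry and AR(1). State that empirical (sandwich) standard errors will be used for any structure other than unstructured. The sandwich standard error is the essential part, because the heterogeneous structures do not fully restore the level on their own.

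The cost is one sentence and slightly more model code. There are two limits: a heterogeneous structure may itself fail to converge, and the sandwich standard error does not remove bias from a misspecified covariance when data are missing at random.
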